3.8.2 Imaging, Treatment Response and Tumor Control Assessment

Patients will undergo brain MRI prior to study entry and at 1 month, 4 months and every 3 months thereafter or when otherwise indicated (eg. at onset of clinical deterioration). A plus or minus 3 week window will be allowed for follow-up imaging and tumor response assessments.

1. Brain metastasis evaluation

The appearance (yes/no) of any new brain metastases will be recorded on all follow-up forms. Any new lesions on follow-up imaging will be defined as progression. Progression will be categorized as described below.

2. Primary Tumor or Resection Cavity response evaluation.

For intact solid tumors, the treated lesion will be evaluated on each follow-up MRI for evidence of progression and response according to the Response Evaluation Criteria for Solid Tumors (RECIST)(**Appendix C**). For resection cavities, residual disease or any new/progressive disease will also be measured. If there is no residual disease or progressive disease, the cavity will be considered stable and no measurements will be taken. New appearance of, or increase in, contrast enhancement of the cavity or surrounding vasogenic edema will be recorded.

3. Any situation where it is unclear whether the imaging changes are due to tumor relapse/progression versus radiation necrosis will require further work-up. This may include MR spectroscopy, MR perfusion, brain PET scan, or a combination of several modalities. In cases in which the patient is symptomatic and an unequivocal diagnosis cannot be made may require surgical intervention

3.8.3 Neurocognitive/Quality of Life Outcome Assessments

All tests will be given at baseline (if the patient consents to completing them) and at every follow-up for the first 7 months, then every 6 months thereafter (at 1, 4, 7, 13, 19, and 25 months).

1. Tests to be administered:

Cognitive Domain	Assessment
Memory	Hopkins Verbal Learning Test-Revised
Global Function	Mini-Mental Status Examination
Cognitive Function (self-report)	Medical Outcomes Cognitive Scale
Quality of Life	Functional Assessment of Cancer Therapy-Brain (FACT-Br)

2. Hopkins Verbal Learning Test- Revised (HVLT-R)

The patient learns 12 words read to them 3 times; free recall is tested after each learning trial. Delayed recall is evaluated after 20 minutes. Following the delayed recall trial, the patient completes a delayed recognition test to determine if an impairment of delayed recall is due to a retrieval deficit or to a consolidation deficit. Entire test requires about 5 minutes to complete, excluding waiting period before delayed recall.

3. Mini-Mental Status Examination (MMSE)

This is a brief, standardized tool to grade patients' global cognitive function. The MMSE begins with an assessment of orientation to place and time. Next is a test of memory (immediate recall) by having the subject immediately repeat the names of 3 objects presented orally. Following this, the patient subtracts sevens serially from 100. The subject is then asked to recall the three items previously repeated (delayed recall). The final section evaluates aphasia and apraxia by testing naming, repetition, compliance with a 3-step command, comprehension of written words, writing, and copying a drawing. The maximum score that can be obtained for the entire MMSE is 30 points.

4. Cognitive Functioning Subscale of the Medical Outcomes Scale (MOS) (Self-report)

This 6-item, self-report measure is designed to measure day-to-day cognitive functioning of which the patient would be aware, including difficulty with problem-solving, slowed reaction times, forgetfulness, and concentration. Reliability and validity have been reported for patients with cancer. Scale is based on multiple choice questions asking about cognitive function where the item is present 1= all of the time to 6=none of the time. Scored in five steps (data cleaning, changing out of range values to missing, item re-calibration and skip pattern recording, reverse scoring of items so that the highest score reflects the best health state, transforming scores linearly to a common metric with a range of 0-100, averaging across items in the same scale). Completion time is estimated to be less than 5 minutes.

5. Functional Assessment of Cancer Therapy-Brain (FACT-Br)

This assessment is a commonly used instrument measuring general quality of life (QOL) reflecting symptoms or problems associated with brain malignancies across 5 scales: physical well-being (7 items); social/family well-being (7 items); emotional well-being (6 items); functional well-being (7 items); and concerns relevant to patients with brain tumors (23 items). Patients rate all items using a five-point rating scale ranging from "not at all" to "very much." The measure yields information about total QOL, as well as information about the dimensions of physical well-being, social/family well-being, emotional well-being, functional well-being, and disease-specific concerns. Six additional experimental items request information regarding how much each dimension affects QOL, using a "0" (not at all) to "10" (very much so) rating scale.

3.8.4 Data Collection

1. Data Fields

The following data will be collected on each patient: name, date of birth, medical record number, laboratory data, tumor characteristics by pathology of surgical specimen, surgical variables, previous radiation variables, radiologic results, performance status, radiation and chemotherapy treatment parameters, clinical outcome including local and distant brain control, recurrence patterns, overall survival, treatment complications, neurocognitive assessments, and QOL assessments.

2. Criteria for patient to be considered a local/marginal failure

- 2.1 Patient requires secondary treatment including surgery or repeat radiation therapy
- 2.2 Unequivocal imaging (contrast MRI) evidence of local recurrence as defined by RECIST criteria. At least a 20% increase in the sum of diameter of the treated lesion or the residual enhancement within the resection cavity, demonstrating at least an absolute increase of 5mm
- 3. Categorization of Recurrence Pattern
 - 3.1 Local failure is defined as evidence of recurrence where >80% of tumor is within prescription isodose line)
 - 3.2 Marginal Failure-is defined as evidence of recurrence where any part of the tumor is within prescription isodose line, but < 80%
 - 3.3 Distant failure is defined as evidence of recurrence within the brain but none of the tumor volume lies within the prescription isodose line.
- 4. Data storage

Each patient will be assigned a study number to be used in data collection and storage so as to protect each patient's PHI. All patients will sign a HIPPA consent for release of PHI. PHI will be destroyed at completion of the study. Study database will be stored on a secure, password protected server in the department of radiation oncology.

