2.2.1 Local control: lack of progression of disease in resection cavity

2.2.2 Distant control: lack of progression of disease in surrounding brain

2.2.3 Overall survival: death from any cause

2.2.4 Long-term neurocognitive outcomes: using the Hopkins Verbal Learning Test–Revised (HVLT-R), Mini Mental Status Exam (MMSE) and Cognitive Functioning Subscale of the Medical Outcomes Scale (MOS).

2.2.5 Quality of life (QOL) outcomes: using the quality of life questionnaire for the Functional Assessment of Cancer Therapy-Brain (FACT-Br).

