3.4.6 Dose Limitation to Critical Structures

1. In addition to the above defined GTVs, CTVs and PTVs, both eyes, the lenses of both eyes, the optic nerves, the optic chiasm, the brainstem and the spinal cord and the whole brain and normal brain parenchyma will be contoured. Normal brain is defined as the whole brain minus the GTV. Dose-volume histograms will be generated and whole organ dose and maximum point dose will be recorded for each critical structure.
2. If the patient has received no prior cranial irradiation, the maximal point doses permissible to the structures from the current radiation therapy plan are listed below* (Table 2).

3. If the patient has received previous WBRT, the previous dose received to critical structures should be obtained or a representative dose distribution file should be simulated. This dose should then be converted to BED (assuming an alpha-beta ratio of 3 for late effects) and added to the BED to the critical structures from the current treatment plan. This sum BED must meet the cumulative dose constraint below[¶] (Table 2). No adjustments for time between previous radiation treatment will be made for the purpose of this protocol.
4. If a patient is recommended to receive whole brain radiation after completion of the study treatment, the constraints listed in Table 3 should be met during the whole brain radiation treatment. It is recommended that the 90% isodose volume from the hypofractionated radiosurgery treatment be created into an avoidance structure and constrained such that the maximum dose to this structure or the normal brain has a cumulative BED₃ of ≤ 150 (equivalent to max dose 15-18 Gy when delivered in 3-3.5 Gy per fraction).

Table 2. Normal Tissue Constraints for Hypofractionated Radiosurgery Treatment

Cumulative BED ₃	Volume	No Previous RT*	Previous RT [¶]
		Maximum Dose	Maximum Cumulative BED ₃
Brainstem	Max, $\leq 0.03\text{cc}$	26 Gy	90
Spinal Cord	Max, $\leq 0.03\text{cc}$	22 Gy	75
Eye (Globe), each	Max, $\leq 0.03\text{cc}$	20 Gy	66
Lens, each	Max, $\leq 0.03\text{cc}$	2.5	12
Optic Nerve, each	Max, $\leq 0.03\text{cc}$	26 Gy	90
Optic Chiasm	Max, $\leq 0.03\text{cc}$	26 Gy	90
Normal Brain	Modal	20 Gy	15 Gy
Normal Brain	$\leq 23\text{ cc}$	4 Gy/fraction	4Gy/fraction

Table 3: Constraints for Whole Brain Radiation following hypofractionated radiosurgery

Cumulative BED ₃	Volume	WBRT after study treatment
		Maximum Cumulative BED ₃
Brainstem	Max, $\leq 0.03\text{cc}$	90

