4.6 Criteria for patient to be considered off study

- 4.6.1 Patient death.
- 4.6.2 Patient undergoes whole brain radiation therapy. However, we will continue to follow the patient after whole brain radiation therapy to document whether there are any enhanced toxicities with the combination of the study treatment and whole brain radiotherapy.
- 4.6.3 Patient request to come off study.

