1. MTD
2. Neurologic toxicity due to treatment
- 5.1.2 Secondary Endpoints
 1. Local Control
 2. Margin Control
 3. Distant brain control
 4. Freedom From Failure/Progression Free Survival
 5. Overall Survival
 6. Neurocognitive effects
 7. QOL outcomes

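### Section 3.8.4 item 2.1 counts secondary surgery or repeat radiation as local/marginal failure without requiring recurrence, so a resection showing only radiation necrosis would be scored as loss of local control (minor)

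*Combined protocol and SAP*

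**What the plan says.** Section 3.8.4 item 2 gives two criteria for calling a patient a local/marginal failure. Item 2.1 reads "Patient requires secondary treatment including surgery or repeat radiation therapy". Item 2.2 begins "Unequivocal imaging (contrast MRI) evidence of local recurrence as defined by RECIST criteria" and adds size thresholds: growth of at least 20% and at least 5 mm. No conjunction joins the two items.

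Item 3 of the same section then sorts recurrences by position relative to the prescription isodose line. For the local category it says "Local failure is defined as evidence of recurrence where >80% of tumor is within prescription isodose line". Marginal and distant failure (3.2 and 3.3) are likewise defined by evidence of recurrence.

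The endpoint itself is defined in section 2.2.1: "Local control: lack of progression of disease in resection cavity". Section 5.1.2 lists local control, margin control and "Freedom From Failure/Progression Free Survival" among the secondary endpoints and does not define the last of these separately. Section 5.3.2.1 plans a Kaplan-Meier analysis of time to local/distant brain progression and a rate at a given time point.

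Section 3.8.2 item 3 deals with imaging changes that could be either tumor or radiation necrosis. It requires further work-up and adds: "In cases in which the patient is symptomatic and an unequivocal diagnosis cannot be made may require surgical intervention". It does not say how the result of that surgery is to be scored for local control.

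**The concern.** Item 2.1 turns on the fact of treatment, while every other definition of the endpoint turns on disease. The two come apart in a situation that the protocol itself anticipates: a symptomatic patient with equivocal imaging is operated on, and the specimen shows necrosis without viable tumor. Under item 2.1 that patient is a local/marginal failure. Under section 2.2.1 disease has not progressed, and under items 3.1 and 3.2 there is no tumor to locate, so the patient fits neither category.

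What is at stake is the meaning of the reported local control, margin control and freedom from failure/PFS. The rule as written would count a complication of the treatment as regrowth of the tumor. In a study that escalates dose, and whose results section 1.0 says may inform later efficacy trials, those two outcomes should be kept apart.

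**Working it through.** **Step 1. Are items 2.1 and 2.2 alternatives?** The text prints neither *and* nor *or*, so both readings have to be tried.
- If both were required, an unequivocal RECIST recurrence that received no surgery or repeat radiation would not be a failure. That contradicts section 2.2.1 and item 3.1.
- If either suffices, untreated recurrences are captured through 2.2. The list then works, except that 2.1 carries no recurrence condition.

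The second reading is the natural one, although the document does not state it.

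**Step 2. Apply each definition to a necrosis-only resection.**

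| Provision | Requires | Result |
|---|---|---|
| 3.8.4 item 2.1 | secondary surgery or repeat radiation | failure |
| 3.8.4 item 2.2 | unequivocal RECIST recurrence on MRI | not a failure, unless the enhancement growth was itself read as recurrence |
| 3.8.4 items 3.1, 3.2 | recurrence located by isodose line | fits neither |
| 2.2.1 | progression of disease | control maintained |

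**Step 3. Size.** The plan states no figure for this, so there is none to reproduce. The inputs do check: 8 cohorts × 3 = 24 patients (sections 3.2 and 5.2), and 3/47 = 6.4% symptomatic necrosis (section 1.0).

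One misclassified patient moves the crude proportion by 1/24 = 4.2 points.

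For an expected count, let
- LC = 0.69, the 6-month local control in the institution's series (section 1.0);
- q = 3/47 = 0.0638, its symptomatic necrosis rate;
- s = the share of those cases operated on before 6 months. The documents do not give it; I assume 0.25 to 1.

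If necrosis is independent of true control, the fraction falsely scored as failure is f = LC × q × s.

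| | s = 0.25 | s = 1 |
|---|---|---|
| f | 0.0110 | 0.0440 |
| Expected patients, 24 × f | 0.26 | 1.06 |
| Chance of at least one, 1 − (1 − f)^24 | 23% | 66% |
| Reported 6-month control, 0.69 − f | 67.9% | 64.6% |

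The shift is therefore 1.1 to 4.4 points. For scale, 0.69 × 24 = 16.6, so take 17/24 (70.8%): its exact 95% interval runs from 48.9% to 87.4%, which is 38.5 points wide.

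**Step 4. Primary endpoints.** DLT is defined by toxicity grade and attribution (sections 2.1.2 and 3.8.1), and MTD is built on DLT. Neither refers to the failure criteria in section 3.8.4, so neither changes.

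**The case against.** The best reply is that the context already supplies the missing condition. Item 2 is headed as local/marginal failure, the endpoint is lack of progression, response is assessed by RECIST, the planned analysis is of time to progression, and item 3 requires recurrence. Investigators review the categorization of failures every month (section 7.2.1), and treatment complications are a separate data field. This makes it likely that salvage of recurrent tumor was intended. It does not settle the matter: item 2.1 still reads as a sufficient criterion, and the monthly review has no rule to apply to a necrosis-only specimen.

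A second reply is that counting any re-intervention as failure is conservative and defensible when tumor and necrosis are hard to separate. It is true that item 2.1 can only lower reported local control, never raise it. But an intervention-based endpoint would need to be named as such; the plan calls this one local control and defines it by disease.

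Third, the size rests on assumptions and leans high. That stands. The upper end needs every symptomatic necrosis case to be operated on by 6 months, and some of those patients may already meet item 2.2, in which case item 2.1 changes nothing or only the event date.

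A reader might also infer that item 2.1 turns later whole brain radiation for new distant lesions into a local failure, since section 3.4.6 item 4 provides for the case "If a patient is recommended to receive whole brain radiation after completion of the study treatment" and section 4.6.2 lists "Patient undergoes whole brain radiation therapy" as an off-study event. The documents do not support resting the point on that. The local/marginal heading supplies a site, item 3.3 assigns recurrence wholly outside the isodose line to distant failure, and *repeat* radiation most naturally means treating the same site again. Naming the treated site in the rewording closes the question anyway.

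**Conclusion.** The point holds at minor severity. As written, and with items 2.1 and 2.2 taken as alternatives, a resection that shows only necrosis is a local failure under item 2.1 and is not one under section 2.2.1 or items 3.1 and 3.2.

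The effect is 4.2 points per patient on descriptive secondary endpoints. In expectation it is at most about 0.3 to 1.1 patients of 24, given the 3/47 rate, the assumed 25-100% operated share, and independence of necrosis from true control. It is smaller if some of these patients already meet item 2.2. Three limits apply. The 3/47 has no stated time horizon. The series does not say how it scored necrosis surgery, so part of the shift may already be inside the 69%. And the count scales in proportion to the necrosis rate, which the documents do not give for the higher dose levels.

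A reader might infer that dose finding, or a comparison of local control between doses, is biased. Neither follows: DLT and MTD do not use these criteria, and the plan contains no comparison of local control by dose. The case for acting is that the endpoint should mean one thing, not that the numbers would move far.

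**What to change.** Reword item 2.1 along these lines: *secondary surgery or repeat radiation to the treated site for recurrence confirmed by pathology or judged unequivocal at the 7.2.1 review*. Add that surgery showing necrosis without viable tumor is recorded as a treatment complication and not as a local failure. Apply the same rule to margin control and freedom from failure/PFS, and report the number of such operations.

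Whether follow-up for local control is censored at such surgery or continued is for the trial statistician to decide. The choice should be written down before outcomes are known, because resection removes the treated site and censoring carries its own assumption about the risk in operated patients.

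The cost is a few lines in section 3.8.4, a line in section 5.3.2.1 for the follow-up rule, and one case report form field for the pathology of any re-operation. No visits, scans or patients are added. The downside is that a few cases may stay indeterminate and will still need judgment at the monthly review.

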4.0 PATIENT SELECTION

4.1 Inclusion Criteria

- 4.1.1 Pathologic proven diagnosis of solid tumor malignancy.
- 4.1.2 Age ≥ 18 .
- 4.1.3 One brain metastasis or brain metastasis resection cavity with maximal diameter ≥ 3 cm (or ≥ 14 cc.) and ≤ 6 cm (or ≤ 113 cc.).
- 4.1.4 RPA class I-II/ Karnofsky Performance Status $\geq 70\%$ (See **Appendix D for definitions**)

4.2 Exclusion Criteria

- 4.2.1 Prior SRS to adjacent lesion such that planning target volume would have received more than 12 Gy
- 4.2.2 RPA class III (KPS < 70%, see **Appendix D definitions**).
- 4.2.3 Brain metastasis or resection cavity volume < 3 cm or 14 cc. or > 6cm or 113 cc.
- 4.2.4 Radiosensitive or non-solid (eg. small cell lung carcinomas, germ cell tumors, leukemias, or lymphomas) or unknown tumor histologies.
- 4.2.5 Concurrent chemotherapy (no chemotherapy starting 14 days before start of radiation).
- 4.2.6 Evidence of leptomeningeal disease by MRI and/or CSF cytology.
- 4.2.7 Current pregnancy
- 4.2.8 More than 8 weeks between resection and radiosurgical procedure
- 4.2.9 Metastases to brain stem, midbrain, pons, or medulla or within 5 mm of the optic apparatus (*optic nerves and chiasm*).
- 4.2.10 Inability to undergo MRI evaluation for treatment planning and follow-up

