In our own experience at Emory¹⁹ with 47 patients receiving HR for both solid intact metastasis (22) and resection cavities (25), we have demonstrated 6 month and 1 year LC rates of 69% (CI 0.62-0.77) and 59% (CI 0.67 – 0.50), with 3 (6.4%) patients experiencing symptomatic radiation necrosis. On multivariate Cox-regression analysis, improved local control was associated with smaller planned target volume (PTV) volume (SS, $p=0.02$) and higher dose per fraction (NS, $p=0.06$). No significant association was found between LC and previous RT received, resection cavity vs. solid tumor, total dose, biological equivalent dose (BED) or single fraction equivalent dose (SFED). These results show HR is well tolerated in both new and recurrent, previously irradiated large intact or resected brain metastases. Significantly higher rates of local failure are observed with larger PTV volumes suggesting a need for dose escalation when using HR for large intracranial lesions.

We propose a prospective phase I trial for patients with solid brain metastasis greater than 3cm and less than 6 cm, who have either had no treatment or who are status post surgical resection. The purpose of this trial will be to determine the maximum tolerated dose for fractionated radiosurgery delivered in 5 fractions with a minimum of 2 and a maximum of 3 fractions being delivered per week. Results from this trial may form the basis of future trials evaluating the efficacy of fractionated radiosurgery regimens for local and distant control of brain metastasis and for directly comparing WBRT with FRS, for patients not amenable to single fraction SRS. Such a phase III study would answer the question about as to whether local irradiation is adequate treatment for patients with large brain metastasis.

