Spinal Cord	Max, $\leq 0.03\text{cc}$	75
Eye (Globe), each	Max, $\leq 0.03\text{cc}$	66
Lens, each	Max, $\leq 0.03\text{cc}$	12
Optic Nerve, each	Max, $\leq 0.03\text{cc}$	90
Optic Chiasm	Max, $\leq 0.03\text{cc}$	90
Dose within 90% isodose line from study treatment or within normal brain	Max, $\leq 0.03\text{cc}$	150

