APPENDIX E

Eligibility Checklist

1. _____ Pathological proven diagnosis of solid tumor malignancy, not a radiosensitive or non-solid (eg. small cell lung carcinomas, germ cell tumors, leukemia, or lymphoma) or unknown tumor histology.
2. _____ Age ≥ 18 .
3. _____ One brain metastasis or brain metastasis resection cavity with maximal diameter greater $\geq 3\text{cm}$ (or $\geq 14\text{ cc.}$) and $\leq 6\text{cm}$.
4. _____ RPA class I-II/ Karnofsky Performance Status $\geq 70\%$ (See **Appendix D for definitions**)
5. _____ No Prior SRS to adjacent lesion such that planning target volume would have received more than 5 Gy
7. _____ No concurrent chemotherapy (no chemotherapy starting 14 days before start of radiation).
8. _____ No evidence of leptomeningeal disease by MRI and/or CSF cytology.
9. _____ Negative serum or urine pregnancy test within 4 weeks of enrollment
10. _____ Less than or equal to 8 weeks between resection and enrollment
11. _____ No metastases to brain stem, midbrain, pons, or medulla or within 5 mm of the optic apparatus (*optic nerves and chiasm*).
12. _____ Patient is able to undergo MRI evaluation for treatment planning and follow-up

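### The prior-SRS exclusion limits earlier dose to the target only when that SRS was aimed at an adjacent lesion; SRS to the index lesion followed by resection is left open

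*Combined protocol and SAP*

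**What the plan says.** Two places restrict earlier SRS. Section 4.2.1 excludes "Prior SRS to adjacent lesion such that planning target volume would have received more than 12 Gy". Appendix E, item 5, requires "No Prior SRS to adjacent lesion such that planning target volume would have received more than 5 Gy". Both are tied to an adjacent lesion.

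Inclusion criterion 4.1.3 defines the target by size alone, with no condition on earlier radiation to it. The background in section 1.0 describes the intended patients as those "who have either had no treatment or who are status post surgical resection". Section 4.2.8 excludes patients treated more than 8 weeks after resection.

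For planning after earlier radiation, section 3.4.6 item 3 begins: "If the patient has received previous WBRT, the previous dose received to critical structures should be obtained". The associated Table 2 column is headed for previous RT in general, but its rows are critical structures and normal brain, and item 1 states: "Normal brain is defined as the whole brain minus the GTV".

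Previously irradiated patients are expected: section 5.3.3.2 plans a stratum for earlier WBRT or other cranial irradiation.

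**The concern.** The purpose of 4.2.1 is evidently to keep out patients whose planning target volume has already had a substantial radiosurgical dose. Yet it acts only on dose that spilled over from a neighbour. A patient with slightly more than 12 Gy of spill is excluded. A patient whose index lesion was itself given a full radiosurgical dose and then resected meets no written exclusion on that account.

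Such a patient would be re-irradiated in the same region at a dose under escalation. Under section 3.8.1 item 6, a grade 3 or higher CNS toxicity that is even possibly caused by radiation is a DLT. Sections 3.2 and 5.3.3 have all patients escalate as one cohort, three at a time. A DLT arising from earlier direct SRS would therefore enter the shared dose decisions. The stratified analysis in 5.3.3 is made only if enrollment allows it, and it protects neither that patient nor those decisions.

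**Working it through.** **Step 1: does any text close the gap?**

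| Text | Covers earlier SRS to the index lesion? |
|---|---|
| 4.1.3 | No. Size only. |
| 4.2.1; Appendix E item 5 | No. Adjacent lesion only. |
| 4.2.8 | No. It limits time since resection, not earlier dose. |
| 1.0, intended population | In effect yes for an intact lesion. Not clearly for a lesion given SRS and then resected, since that patient has still had a resection. It is background text and sets no dose limit. |
| 3.4.6 item 3 | No. It names earlier WBRT and concerns critical structures. |
| Table 2, previous-RT column | No limit on the target, even if read to include SRS, because normal brain excludes the GTV. |

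Checklist item 6 and Appendix H are not in the text available. Section 4.2 is numbered without gaps and has no such rule.

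**Step 2: reproduce the plan's BED3 figures.** The formula is BED3 = n × d × (1 + d/3), with n fractions of d Gy and the alpha-beta ratio of 3 from section 3.4.6.

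- Level -1: 5 × 5.5 × (1 + 5.5/3) = 77.9 (Table 1: 78)
- Level 0: 5 × 6 × (1 + 6/3) = 90 (Table 1: 90)
- Level 4: 5 × 8 × (1 + 8/3) = 146.7 (Table 1: 147)
- SRS row, 18 Gy: 18 × (1 + 18/3) = 126; 21 Gy: 21 × (1 + 21/3) = 168 (Table 1: 126-168)

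The formula agrees with Table 1.

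**Step 3: compare the limit with direct SRS.** Section 4.2.1 gives no fraction number; I read 12 Gy as one fraction.

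- Limit: 12 × (1 + 12/3) = 60
- Direct SRS, assumed 18-21 Gy: 126/60 = 2.1 and 168/60 = 2.8

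**Step 4: hypofractionated courses.** Section 1.0 cites a definition under which SRS includes courses of 2-5 fractions, and describes three such regimens:

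- 24 Gy in 4: 4 × 6 × (1 + 6/3) = 72
- 24 Gy in 3: 3 × 8 × (1 + 8/3) = 88
- 30 Gy in 5: 90

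At prescription dose, all three exceed 60. A reworded criterion therefore needs a BED3 form as well as a single-fraction dose.

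**The case against.** **The gap is narrow.** The population statement in section 1.0 reads naturally as allowing resection as the only earlier treatment of the target. A reader might infer that intact lesions with earlier SRS are freely admissible; the documents do not support that. This stands, and it reduces the point to SRS followed by resection. Section 1.0 also says that single-fraction SRS is typically used below 3 cm, which makes the sequence less common still.

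**The intent is obvious.** A screener who must exclude spill above 12 Gy would probably judge direct SRS the same way. Under section 4.4 the screener is a radiation oncologist, and section 3.8.4 records earlier radiation. This lowers the likelihood of harm, but the written criteria still contain no such rule.

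**The surrounding tissue is not unaddressed.** Section 3.4.6 item 2 reserves the first Table 2 column for patients without earlier cranial irradiation, so a patient with earlier SRS would fall to the other column. For a cavity, the adjoining brain outside the GTV is normal brain and meets those rows. This is fair, but the normal-brain rows (a modal dose and a per-fraction dose to a volume) do not set a clear cumulative limit on the target.

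**Re-irradiation is a disclosed choice.** Section 1.0 reports hypofractionated treatment as well tolerated in "recurrent, previously irradiated large intact or resected brain metastases", without saying how many or after which earlier radiation. That choice is not disputed here. The point is only that the plan's own threshold is applied to one source of dose and not the other.

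**The protocol's limit of 150 does not measure this gap.** Table 3 sets a maximum cumulative BED3 of 150 for "Dose within 90% isodose line from study treatment or within normal brain". A reader might add 126-168 to the study course and infer a breach of the protocol's own limit. The documents do not support that. Table 3 governs WBRT given after study treatment and is a maximum-dose limit (0.03 cc or less), not a prescription-dose limit. The study course alone can exceed it:

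- Level 3 with the 10% inhomogeneity allowed in section 3.4.4: 41.25 Gy in 5, 41.25 × (1 + 8.25/3) = 155
- Level 4 likewise: 44 Gy in 5, 44 × (1 + 8.8/3) = 173
- Level -1 with a 50% Gamma Knife prescription: maximum 55 Gy in 5, 55 × (1 + 11/3) = 257

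Even the 12 Gy limit, added to the study course at prescription dose, passes 150 from level 1 (60 + 103 = 163) to level 4 (60 + 147 = 207). So 150 does not distinguish the patients at issue.

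**Conclusion.** The concern holds in a narrow form. As written, the prior-SRS rule excludes a patient for dose received from a neighbouring lesion, and sets no limit when a dose of 2.1-2.8 times that BED3 was aimed at the index lesion and the lesion was then resected. It is probably a drafting gap.

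The ratio rests on three assumptions: 12 Gy is a single fraction; the earlier SRS was 18-21 Gy, taken from a row that Table 1 labels as comparison only; and the planning target volume received that dose. If the earlier target was smaller than the present one, part of the volume received less, and resection removes at least some of the irradiated tissue. The ratio therefore describes the wording, and does not estimate dose in actual patients.

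A reader might also infer that the MTD would be biased. The documents give no frequency for this sequence and no basis for estimating its effect on DLTs, so that cannot be claimed. Both are probably small. Severity: minor safety wording correction.

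**What to change.** Reword 4.2.1 and Appendix E item 5 to exclude any earlier SRS or hypofractionated course, whether to the index lesion, its cavity or an adjacent lesion, that gave the planning target volume more than the existing threshold: 12 Gy in a single fraction, or BED3 60 for a multi-fraction course.

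Use the same number in both places. The present difference between 12 Gy in 4.2.1 and 5 Gy in the checklist is a separate inconsistency and adds no weight to this point, but the same edit can settle it. If the clinical team prefers 5 Gy, the matching figure is BED3 13.3, from 5 × (1 + 5/3).

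The cost is one sentence in each place. The downside is that a few previously radiosurgically treated patients become ineligible.
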